5. **Cost-effectiveness analysis:** To determine the cost effectiveness of Botox A injection versus mid-urethral sling for the treatment of MUI symptoms on an intent-to-treat basis 6 months post-treatment.
6. **UDI MID:** To explore MIDs for UDI total score and stress and irritative subscores for this MUI population.

The MUSA study was initially designed as a 12 month study, however due to constraints related to funding and completing the study within the current PFDN cycle, the study was revised to a 6 month outcome. The DSMB recommended a 12 month follow up. 12 month outcomes are common in midurethral sling surgical

trials and a similar outcome to the ESTEEM study. The PFND bridge year funding now allows us the opportunity to extend the MUSA trial to 12 month outcomes.

MUSA recruitment began in July 2020 and was estimated to be completed by May 2021, by the end of the current PFDN cycle. The bridge year would extend until June 2022 and allow completion of the 12 month MUSA outcome within the bridge year. The first MUSA subject 9-month and 12-month windows would open Apr 2021 and August 2021, respectively. The current cycle ends in June 2021, if the MUSA 12 month follow-up needs to be discontinued due to time or financial reasons, there would be a potential of 9, 9-month calls and no 12-month calls completed before June 2021.

Proposed Extension of Study

This amendment proposes to continue to follow all the MUSA subjects from 6 to 12 months. **The 6-12 month extension would be observational.** Participants would be allowed to pursue other clinical treatments after 6 months, including the alternative arm treatment. **The primary MUSA study outcome remains at 6 months. The 12-month aims, outcomes, outcome measures, and analysis are similar to the existing MUSA study at 6 months.**

12-month aim: To compare the effectiveness of intradetrusor injection of 100 units of Botox A to mid-urethral sling for change in MUI symptoms 12 months following treatment.

Primary Outcome: Change in severity of MUI symptoms 12 months post treatment measured using the UDI

Secondary Outcomes: Change in severity of SUI and UUI symptoms 12 months post treatment measured using the stress and irritative subscales of the UDI

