5.3 Safety (SAF) Population

The safety population will comprise all subjects who were randomized and treated, grouped by the treatment to which they actually received (for any situations in which a participant was not initially treated with their randomized treatment assignment). If all patients received their randomized treatment and have some post-baseline efficacy data, then the safety population would be the same as the mITT.

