		Indicators will be created for overall additional treatment and the following individual categories:
		Up to 6 months (up to the day before the 6 months visit):
		MUS for Botulinum toxin A arm
		Botulinum toxin A for MUS arm
		OAB/UUI medication
		Behavioral Therapy
		Physical Therapy / Biofeedback
		PTNS
		Continence pessary / POISE Impressa
		Sacral neuromodulation
		Bulking injections
		6-12 months (starting the day of the 6 months visit)
		Mid-urethral Sling placement

Variable	Туре	Definition
		Botulinum toxin A injection
		OAB/UUI medication
		Behavioral Therapy
		Physical Therapy / Biofeedback
		PTNS
		Continence pessary / POISE Impressa
		Sacral neuromodulation
		Bulking injections
Safety outcomes		Adverse events are reported for a participant from the date they are randomized to the date that they exit the study. There were 9 adverse events that were collected after randomization but occurred before treatment. The majority of these were UTIs (n=8), with one "Fall" event that is important documentation leading into a subsequent serious adverse event.
Sling Revision or removal at	Dichotomous	An indicator of sling revision/removal will be calculated for each subject where those
any time	1=yes 0=no	who have a sling revision/removal listed on the Additional Therapy form will be assigned a "Yes", otherwise subjects are assigned "No".
		At final database lock reviews, one "sling removal" was identified from the Additional Therapy form. Adverse events were further reviewed for implemented actions of "explant" or "surgical intervention" but yielded no further cases identified. An adverse event form was requested to be entered for the single reported removal.
		The rate of sling revision is calculated as the percentage of participants with indicator equal to "Yes" among all non-missing indicators.

Variable	Туре	Definition
Sling mesh exposure	Dichotomous 1=yes 0=no	An indicator of sling mesh exposure will be calculated for each subject (yes/no) using the MEDRA coded preferred term of reported adverse events. Subjects will be coded to "Yes" if they have any adverse event with a MEDRA preferred term of "Medical device site erosion", or if the verbatim adverse event term includes text strings "Mesh", "Mesh exposure", or "MUS mesh exposure". Two cases were identified from adverse event forms at final database lock review.

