Rate of Urinary Tract Infection (UTI) Events	Dichotomous 1=yes 0=no	The frequency of acute UTI events will be taken from all adverse event reporting forms submitted for a participant. The outcome variable will be coded with a value of "Yes" if the participant had any reported acute UTIs over their study duration, identified by MEDRA coding preferred term of "Urinary tract infection" and "recurrent" is NOT specified by verbatim adverse event term or comments. If no acute UTI events were reported for a participant, the outcome variable will be coded with a value of "No".Final database lock review took efforts to query sites for participants with questionable urine test results and get PI confirmation that all necessary events had been reported.
Rate of recurrent Urinary Tract Infection (UTI) Events	Dichotomous 1=yes 0=no	The frequency of recurrent UTI events will be taken from all adverse event reporting forms submitted for a participant. The outcome variable will be coded with a value of "Yes" if the participant had any reported recurrent UTIs over their study duration, identified by MEDRA coding preferred term of "Urinary tract infection" and "recurrent" is specified by verbatim adverse event term or comments. If no recurrent UTI events were reported for a participant, the outcome variable will be coded with a value of "No". Final database lock review took efforts to query sites for participants with questionable urine test results and get PI confirmation that all necessary events had been reported.
Rate of Urinary Retention Events	Dichotomous 1=yes 0=no	The frequency of urinary retention events will be taken from all adverse event reporting forms submitted for a participant. The outcome variable will be coded with a value of "Yes" if the participant had any reported urinary retention over their study duration,

Variable	Туре	Definition
		identified by MEDRA coding preferred term of "Urinary retention". If no urinary retention events were reported for a participant, the outcome variable will be coded with a value of "No".
		Final database lock review took efforts to query sites for participants with reported self- catheterization logs or questionable post void residual results (>200mL, aside from visits immediately post-surgery) and get PI confirmation that all necessary events had been reported.

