Rate of AE of "residual Urine Volume"	Dichotomous 1=yes 0=no	The frequency of residual urine volume events will be taken from all adverse event reporting forms submitted for a participant. The outcome variable will be coded with a value of "Yes" if the participant had any reported residual urine events over their study duration, identified by MEDRA coding preferred term of "Residual urine volume". If no residual urine volume events were reported for a participant, the outcome variable will be coded with a value of "No".
		Final database lock review took efforts to query existing adverse events with terms such as "incomplete bladder emptying", "sensation of incomplete bladder emptying" for any post void residual assessments completed around the time of the event. Details from query responses helped with MEDRA coding the relevant level of severity ("Urinary Retention" vs. "Residual urine volume") accurately.
Complications after study intervention And Complication after cross- over study intervention	Dichotomous 1=yes 0=no	The frequency of complications after study intervention will be taken from Surgeon's Report forms submitted for a participant, for both the main study treatment and allowed Botox reinjection if applicable. The outcome variable for each specific complication will be coded with a value of "Yes" if ever reported over their study duration, otherwise it will be coded with a value of "No". If a participant experienced any complication after main study interventions, the composite indicator will be coded with a value of "Yes", otherwise coded to "No".
Bladder Injury Ureteral Injury		The frequency of complications after cross-over study intervention will be taken from any Off Protocol Surgeon's Report forms submitted for a participant The outcome

Variable	Туре	Definition	
Urethral Injury Vaginotomy		variable for each specific complication will be coded with a value of "Yes" if ever reported over their study duration, otherwise it will be coded with a value of "No". If a participant experienced any complication after a crossover study intervention, the composite indicator will be coded with a value of "Yes", otherwise coded to "No".	
		Note that all reported intervention complications are expected to have an accompanying adverse event form entered but may not be recorded as an adverse event to reduce database redundancy.	

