10 SAFETY ANALYSES

10.1 Overview of Safety Analysis Methods

All safety analyses will be performed using the Safety population unless otherwise specified, consisting of all randomized and treated participants, summarized by the treatment actually received in the case of patients not receiving their randomized treatment. Descriptive p-values comparing the study arms will be provided on most safety table summaries and will be obtained using chi-square tests or Fisher's exact tests (in the case of small numbers of events) for binary outcomes.

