10.2 Adverse Events/Complications/Adverse Symptoms

MUSA complications are divided into "adverse symptoms" and "adverse events".

Participants were asked to report any adverse events or adverse symptoms from randomization through 12 months follow-up. All adverse events were collected on an adverse event log and coded using MedDRA (V24.0). In addition, a few adverse symptoms are captured as part of the PRO questionnaires.

Adverse symptoms will be captured using an active approach using validated questionnaires and an open-ended approach.

- a. Active capture for specific patient-reported adverse symptoms will be identified by responses on validated questionnaires These 3 adverse symptoms are patient report of new or worsening: 1) pelvic/vaginal pain, 2) sensation of incomplete bladder emptying (based on UDI responses) and 3) dyspareunia (based on PISQ-IR response). These are captured at 3, 6, 9, and 12 months.
- b. Open-ended capture for adverse symptoms will also be captured using the open-ended approach and recorded on the AE log. Symptoms of interest include: 1) New/worsening partner dyspareunia and 2) New/worsening constipation. Using the open-ended approach, symptoms are captured if reported by the participant and documented on the Adverse Event log.

Adverse events will be captured using the standard AE open-ended capture approach using chart review, physician report, or patient report corroborated by medical documentation and recorded on the Adverse Event log.

A table summarizing the Adverse Events and Adverse symptoms of interest is as follows (all variable definitions are included in Section 9.2):

Postoperative complications	
Adverse symptom	Definition
*New/worsening abdominal/genital pain at or beyond 3 month visit	UDI item N captured at 3, 6, 9, and 12 months and per patient report, chart review, physician report
*New/worsening dyspareunia at or beyond 3 month visit	PISQ item C5 captured at 3, 6, 9, and 12 months and per patient report, chart review, physician report
*New/worsening report of difficulty emptying bladder at or beyond 3 months	UDI item J captured at 3, 6, 9, and 12 months and per patient report, chart review, physician report
New/worsening partner dyspareunia at or beyond 3 month visit	Per patient report, chart review, physician report

Adverse Event	
Postop need for catheter and/or ISC at or beyond 2 weeks (sling or Botox)	Captured by chart review, physician report, exam, or patient report corroborated by medical documentation

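### Safety events are grouped by first treatment and counted to 12 months, so most safety rates mix the randomised 6 months with events after cross-over

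*SAP*

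**What the plan says.** **Grouping.** SAP 5.3 takes all randomised and treated women, "grouped by the treatment to which they actually received (for any situations in which a participant was not initially treated" as allocated). Only the first treatment can move a woman out of her randomised arm. SAP 10.1 adds: "All safety analyses will be performed using the Safety population unless otherwise specified".

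**Cross-over.** The protocol addendum (section 10, Proposed Extension of Study) says: "Participants would be allowed to pursue other clinical treatments after 6 months, including the alternative arm treatment". SAP 7.4 says the same, and treats other incontinence treatment before 6 months as a protocol deviation.

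**Time span.** SAP 10.2: "Participants were asked to report any adverse events or adverse symptoms from randomization through 12 months follow-up". SAP 9.2, safety outcomes: "Adverse events are reported for a participant from the date they are randomized to the date that they exit the study". Retention is coded yes "if the participant had any reported urinary retention over their study duration". UTI, recurrent UTI, residual urine, pelvic pain, dyspareunia and levator syndrome are defined in the same way. Catheterisation has a lower limit of two weeks after the procedure and no upper limit. Self-reported pain and emptying symptoms use any post-baseline questionnaire. The adverse event tables in SAP 10.2 are by treatment group, with no split by period.

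**The one exception.** SAP 9.2: "The frequency of complications after cross-over study intervention will be taken from any Off Protocol Surgeon's Report forms submitted for a participant". This covers bladder, ureteral and urethral injury and vaginotomy.

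**The concern.** Exploratory aim 5 in SAP 3.1.2 and the safety outcomes in SAP 3.2.4 concern sling revision after a sling, catheterisation after Botox, and a comparison of UTI and other events between groups. Readers will take the resulting rates as the harms of each procedure, or as the randomised comparison. As defined, they are neither. A sling woman who has Botox in month 7 and then needs a catheter is counted in the sling group. If the two-week limit in the catheterisation variable runs from her first procedure, even a short catheterisation straight after the second one qualifies.

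The SAP already separates cross-over for operative injuries, and it tabulates additional treatments separately before and after 6 months. It does not do this for the other harms. The protocol's own safety comparison (6.2.3, aim 4) was written for a 6-month trial. The SAP merges the two periods and specifies no 0–6 month safety table, so the only safety comparison within the randomised period is lost.

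**Working it through.** The documents give no safety sample size and no cross-over rate, so there is no stated figure to reproduce. The point rests on the definitions above. The arithmetic only shows how far a rate could move.

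**Inputs**
- UTI: 24% after sling (ESTEEM, sling only) and 33% after Botox 100 units (ABC), from protocol Table 3.
- Catheterisation: 2% after sling (ESTEEM, catheter after 2 weeks, protocol Table 4) and 6.5% after Botox 100 units (protocol Table 13).
- 73 women per arm (SAP 6).
- Assumed: 10–30% cross over in each direction, all second-procedure events fall within follow-up, and first- and second-procedure events are independent.

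**Formula.** Observed risk in a first-treatment group = 1 − (1 − p_first)(1 − c × p_second), where c is the share crossing over. With equal c in both arms the gap becomes (p_Botox − p_sling)(1 − c).

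**Worked cases for UTI**
- 10% Botox to sling, 30% sling to Botox: Botox group 1 − 0.67 × (1 − 0.10 × 0.24) = 34.6%; sling group 1 − 0.76 × (1 − 0.30 × 0.33) = 31.5%; gap 3.1 points.
- 30% Botox to sling, 10% sling to Botox: Botox group 1 − 0.67 × (1 − 0.30 × 0.24) = 37.8%; sling group 1 − 0.76 × (1 − 0.10 × 0.33) = 26.5%; gap 11.3 points.

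| Botox→sling | Sling→Botox | UTI: Botox / sling / gap | Catheter: Botox / sling / gap |
|---|---|---|---|
| 0% | 0% | 33.0 / 24.0 / 9.0 | 6.5 / 2.0 / 4.5 |
| 10% | 10% | 34.6 / 26.5 / 8.1 | 6.7 / 2.6 / 4.1 |
| 20% | 20% | 36.2 / 29.0 / 7.2 | 6.9 / 3.3 / 3.6 |
| 30% | 30% | 37.8 / 31.5 / 6.3 | 7.1 / 3.9 / 3.2 |
| 10% | 30% | 34.6 / 31.5 / 3.1 | 6.7 / 3.9 / 2.8 |
| 30% | 10% | 37.8 / 26.5 / 11.3 | 7.1 / 2.6 / 4.4 |

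**In women, at 73 per arm**
- Added to the sling group: 73 × c × 0.33 × 0.76 = 1.8 to 5.5 UTI cases, and 73 × c × 0.065 × 0.98 = 0.5 to 1.4 catheterisations.
- Added to the Botox group: 73 × c × 0.24 × 0.67 = 1.2 to 3.5 UTI cases, and 73 × c × 0.02 × 0.935 = 0.1 to 0.4 catheterisations.

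**Sensitivity to the event rate.** Protocol Table 3 lists UTI rates after Botox 100 units from 4.8% to 36%, and Table 16 gives 18% within 12 weeks. At 18% the no-cross-over gap is 18 − 24 = −6 points, and equal cross-over of 10–30% gives −5.4 to −4.2.

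**Mesh.** SAP 9.2 codes mesh exposure for every subject with no time limit. SAP 10.2 labels mesh exposure, mesh erosion and reoperation as applying to the sling only, without saying whether that means the sling group or any woman with a sling.

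**The case against.** The other side has five fair arguments.

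1. Grouping by first treatment is a legitimate 12-month comparison of treatment strategies, and the addendum calls months 6–12 observational and plans a by-group safety comparison at 12 months. This stands as a reason to keep the 12-month table. But the SAP never labels it a strategy comparison, and its outcomes are worded by procedure.
2. A reader might infer that every event after cross-over is charged to the wrong treatment. The documents do not support that, because a late event may still stem from the first procedure.
3. A reader might infer that cross-over must pull the two harm profiles together. That holds for equal cross-over, but with more Botox-to-sling than sling-to-Botox cross-over the UTI gap in the illustration widens.
4. A reader might infer that mesh events will appear under Botox. SAP 10.2's label leaves open that they would be dropped instead. The numbers are small in any case: at database lock SAP 9.2 reports two mesh exposures and one sling removal in the whole trial.
5. The event rates come from trials with different definitions and follow-up. Residual volume and urine dip are not scheduled at 9 and 12 months, so the illustration may overstate the events detected then.

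All of this limits the size and direction of the claim. None of it supplies a 0–6 month safety comparison or separates events after a second procedure.

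**Conclusion.** The concern holds as a matter of definition: apart from the Surgeon's Report complications, no safety variable is cut at, or split by, a second procedure. The resulting rates describe neither the randomised 6 months nor a single procedure. The size is unknown. On the illustrative rates and 10–30% cross-over, a 9-point UTI gap could be reported as anything from about 3 to 11 points, and a 4.5-point catheterisation gap as about 2.8 to 4.4. These figures rest on assumed cross-over and borrowed event rates; they are not forecasts. Stakes are moderate: safety p-values are descriptive (SAP 7.8 and 10.1), and a reader should not infer any effect on the 6-month primary efficacy result. The change is worth making because it is cheap and restores the safety comparison for the randomised period.

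**What to change.** In SAP 5.3, 9.2 and 10:

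- **(a) Randomised period.** Add a by-arm comparison of each safety variable from the first study procedure to the 6-month visit, with events after any earlier cross-over flagged.
- **(b) Full 12 months.** Keep the 0–12 month table by first treatment, labelled as a treatment-strategy summary. Tabulate events with onset after a cross-over procedure separately, as after both procedures, by sequence (sling then Botox, Botox then sling). Do not assign them to the most recent procedure: that would count a late sling harm, such as mesh exposure or dyspareunia, against Botox.
- **(c) Sling-specific events.** Count mesh exposure, erosion, and revision or removal among all women who received a sling, and reconcile the sling-only label in 10.2 with the every-subject coding in 9.2.
- **(d) Catheterisation.** State from which procedure the two-week limit runs.

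The SAP already relies on event timing relative to the procedure, the Additional Therapy form and the Off Protocol Surgeon's Report forms, so no new data should be needed. The cost is wording, programming and one or two more descriptive tables, with small numbers after cross-over.

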6 SAMPLE SIZE DETERMINATION

MUSA will randomize 146 women to treatment with Botox or Sling in a 1:1 ratio. The sample size was derived to provide sufficient power for the primary Aim (comparison of Botox versus sling after 6 months) assessed for the primary outcome (change in UDI total score).

For the primary outcome (UDI total score change from baseline at 6 months), alpha was set at 0.05 and power was set at 90%.

Sample size estimates were based on an evaluation of minimum important differences (MIDs) and corresponding standard deviation (SD) for the UDI total score from the ESTEEM study of MUI, with support from other published populations of women with urge and stress incontinence; however, the populations on which those MIDs were based might differ from the target population of mixed incontinence for MUSA. Thus, our goal was to power the study to detect a statistically significant difference between groups in change from baseline in UDI total score at 6 months for the UDI MID determined from ESTEEM as that will be a clinically important difference in our population. To use the most accurate standard deviation applicable to MUSA, we calculated the SD based on a mixed effects repeated measures model with adjustment for baseline UDI score and clinical site rather than the SD of the observed data in order to account for improvements in variance estimation from the covariate adjustment planned for MUSA. To most closely match MUSA, this analysis model included all 3-month and 6-month ESTEEM data points after any retreatments and excludes patients with <4 Urge IEs/3 days. The MID for ESTEEM UDI-Total is 26, and the SD=46.5 from the analysis model, resulting in an effect size = 0.56.

Total number of randomized patients required to meet planned power estimates were adjusted for the assumed patient discontinuation rate at 6 months. Based on average estimates from ROSETTA and ESTEEM, we plan for 5% discontinuation rate by 6 months.

The evaluable sample size required at 6 months for 90% power for the primary total UDI outcome is 69 per arm. Because data from ROSETTA and ESTEEM suggests that follow-up at 6 months should be about 95%, a total sample size of 73 randomized per treatment arm is selected (69/0.95 =73), for a total sample size of 146 randomized participants.

With the sample size of 146 subjects and the planned standard deviation of 46.5, our study will have 82% power to detect a statistically significant difference in UDI-total score at p<0.05 if the true difference is as small as 23 points (0.50 effect size) between groups at 6 months. Thus, the planned sample size may allow for analyses to assess whether the true MID in this population is smaller than 26.

Assuming an additional 5% discontinuation rate between 6 and 12 month, the study will have 88% power for the 12 month UDI total score outcome based on the MID of 26, and the SD of 46.5.

